endpoint is the change in DAS28-4 (ESR) from randomization (at Week 24) to the end of double-blind MTX withdrawal phase (at Week 48).

STATISTICAL METHODS

Based on estimated CDAI-defined low disease activity rate of 40% derived from prior Phase 3 studies and factoring in a discontinuation rate of approximately 15% during the open label run-in phase, approximately 680 subjects will be enrolled to the run-in phase with the aim of at least 232 subjects being randomized into the blinded MTX withdrawal phase at Week 24. With a two-sided Type-I error of 5% and an assumed standard deviation (SD) of 1.4 for the difference in change from randomization in DAS28-4 (ESR) between the two arms, a sample size of 232 subjects randomized at Week 24 would provide 90% power to declare non-inferiority of tofacitinib monotherapy relative to tofacitinib plus methotrexate with a non-inferiority margin of 0.6.

The primary endpoint of change from randomization in DAS28-4 (ESR) at Week 48 will be analyzed as a continuous variable using a linear mixed-effect model of repeated measures (MMRM) that includes the fixed effects of treatment, visit, treatment-by-visit interaction, prior use of a biological DMARD, and baseline DAS28-4 (ESR) value as a covariate. Within-subject variability will be accounted for using a random effect with an unstructured covariance matrix. Change from randomization at any visit post-randomization will be defined as the DAS28-4 (ESR) value at that visit minus the value at randomization.

The analysis will be based on the Full Analysis Set (FAS), which is defined as those subjects who received at least one dose of tofacitinib MR 11mg plus MTX during the open label run-in period, and were randomized and received at least one dose of the randomized investigational drug regimen (tofacitinib MR 11mg with MTX or tofacitinib MR 11mg with placebo for MTX) during the blinded MTX withdrawal period.

A robustness analysis based on a per-protocol analysis set will be performed. Sensitivity analyses using different methods of handling missing data will also be conducted; further details will be outlined in the SAP.

STATISTICAL DECISION RULES

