6.3. Subject Withdrawal

Subjects may withdraw from the study at any time at their own request, or they may be withdrawn at any time at the discretion of the investigator or sponsor for safety or behavioral reasons, or the inability of the subject to comply with the protocol-required schedule of study visits or procedures at a given study site. A complete list of specific discontinuation criteria for this study is listed in [Section 7.23](#).

If a subject does not return for a scheduled visit, every effort should be made to contact the subject. All attempts to contact the subject and information received during contact attempts must be documented in the subject's medical record. In any circumstance, every effort should be made to document subject outcome, if possible. The investigator should inquire about the reason for withdrawal, request that the subject return all unused investigational product(s), request that the subject return for a final visit, if applicable, and follow up with the subject regarding any unresolved adverse events (AEs).

If a subject completely withdraws from the study, and also withdraws consent for disclosure of future information, no further evaluations should be performed, and no additional data should be collected. The sponsor may retain and continue to use any data collected before such withdrawal of consent.

If a subject has discontinued investigational product for greater than 14 consecutive days, the subject will be discontinued from the study.

Subjects who experience a single episode of disease flare at any time during the study (including the open-label run-in and double-blind phase) that could not be controlled by rescue medications will be discontinued from the study.

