2 sequential AST or ALT elevations ≥ 3 x ULN with an elevated INR	Treatment with all study drugs will be discontinued and the subject withdrawn from this study.
2 sequential AST or ALT elevations ≥ 3 x ULN accompanied by symptoms consistent with hepatic injury	Treatment with all study drugs will be discontinued and the subject withdrawn from this study.
2 sequential AST or ALT elevations ≥ 5 x ULN, regardless of Total Bilirubin or accompanying symptoms	Treatment with all study drugs will be discontinued and the subject withdrawn from this study.
Two sequential hemoglobin values < 8.0 g/dL or a decrease of more than 30% from baseline value;	Treatment with all study drugs will be discontinued and the subject withdrawn from this study. Follow up to resolution
Two sequential platelet counts $< 75,000$ platelets/mm ³ ;	Treatment with all study drugs will be discontinued and the subject withdrawn from this study. Follow up to resolution
2 sequential neutrophil counts < 1000 cells/mm ³	Treatment with all study drugs will be discontinued and the subject withdrawn from this study. Follow up to resolution
Confirmed lymphocyte counts < 500 lymphocytes/mm ³ by repeat testing	Treatment with all study drugs will be discontinued and the subject withdrawn from this study. Follow up to resolution
Confirmed increases in serum creatinine $> 50\%$ over the average of screening and baseline values and the absolute value of serum creatinine is above upper limit of normal range.	Treatment with all study drugs will be discontinued and the subject withdrawn from this study. Retesting should occur until the serum creatinine is within 10% of the pretreatment value.
Serious infections defined as any infection (viral, bacterial, or fungal) requiring parenteral antimicrobial therapy or hospitalization for treatment, or meeting other criteria that require the infection to be classified as a serious adverse event.	Treatment with all study drugs will be discontinued and the subject withdrawn from this study
Opportunistic infection, including tuberculosis, judged significant by investigator	Treatment with all study drugs will be discontinued and the subject withdrawn from this study
Malignancies excluding adequately treated non melanoma skin cancer (NMSC) and cervical carcinoma in situ	Treatment with all study drugs will be discontinued and the subject withdrawn from this study

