Pregnancy or refusal to use appropriate contraception	Permanently withdraw the subject from the study and follow any pregnancy to resolution.
Use of rescue medications for more than 10 consecutive days	Treatment with all study drugs will be discontinued and the subject withdrawn from this study (see Appendix 6 for details).
Anaphylactic or other serious allergic reaction	Immediately discontinue study drug and institute appropriate therapy.
Symptoms suggestive of a lupus-like syndrome	Discontinue study drug and institute appropriate therapy
Other Triggered Requirements for Monitoring	
Condition	Action
Increase lipid parameters (total cholesterol, LDL cholesterol, HDL cholesterol, triglycerides)	Monitor and treat according to local guidance (eg, diet and behavior modification, statin therapy)
Surgery	Interrupt study drug 1 week prior to a scheduled surgical procedure and may resume when operative site is sufficiently healed and risk of infection is minimal. (Study drug administration can be resumed only if the off-drug period is ≤14 consecutive days.)
Use of potent CYP3A4 and CYP2C19 Inhibitors and CYP3A4 Inducers	Treatment with potent CYP3A4 inhibitors or with medications that are both a moderate CYP3A4 inhibitor and potent inhibitor of CYP2C19 require that tofacitinib is interrupted during treatment. Treatment with a potent CYP3A4 does not require tofacitinib discontinuation but should be noted as a protocol deviation. See Appendix 3 for a list of CYP3A4 and CYP2C19 Inhibitors and CYP3A4 Inducers.
ALT = alanine aminotransferase; AST = aspartate aminotransferase; g/dL = grams per deciliter; GGT = gamma-glutamyl transpeptidase, HDL= high density lipoprotein; LDL= low density lipoprotein; PT/INR = Prothrombin Time International Normalized Ratio; mm = millimeter; x ULN = times the upper limit of normal	

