9.1. Sample Size Determination

Based on estimated CDAI-based low disease activity rate of 40% derived from prior phase 3 studies and factoring in a discontinuation rate of approximately 15% during the open label run-in phase, approximately 680 subjects will be enrolled to the run-in phase with the aim of at least 232 subjects being randomized into the blinded MTX withdrawal phase at Week 24. With a two-sided Type-I error of 5% and an assumed standard deviation of 1.4 for the difference in change from randomization in DAS28-4 (ESR) between the two arms, a sample size of approximately 232 subjects randomized at Week 24 would provide 90% power to declare non-inferiority of tofacitinib monotherapy relative to tofacitinib plus methotrexate with a non-inferiority margin of 0.6.

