9.3. Efficacy Analysis

9.3.1. Analysis of the Primary Endpoint

The primary endpoint of change from randomization in DAS28-4(ESR) at Week 48 will be analyzed as a continuous variable using a linear mixed-effect model of repeated measures (MMRM) that includes the fixed effects of treatment, visit, treatment-by-visit interaction, prior use of a biological DMARD, and baseline DAS28-4 (ESR) value as a covariate. Within-subject variability will be accounted for using a random effect with an unstructured covariance matrix. Change from randomization at any visit post-randomization will be defined as the DAS28-4 (ESR) value at that visit minus the value at randomization.

The primary analysis will be a non-inferiority test to show that tofacitinib MR 11mg QD monotherapy is not less effective (non-inferior) than tofacitinib MR 11mg QD with MTX within the margin of non-inferiority set at 0.6 (ie, the difference in mean change from randomization in DAS28-4 (ESR) between the two arms). In other words, the change from randomization in DAS28-4(ESR) for the tofacitinib MR 11mg QD monotherapy arm may be less favorable than that for the tofacitinib MR 11mg QD with continued MTX arm by no more than 0.6. The estimated treatment difference and the associated 95% confidence interval (CI) will be presented. If the upper bound of the 95% two-sided CI for the difference (tofacitinib monotherapy arm minus tofacitinib with MTX arm) in change from randomization in DAS 28-4 (ESR) between the two arms is lower than 0.6, then tofacitinib monotherapy will be declared to be non-inferior to the tofacitinib with continued MTX treatment.

The analysis will be based on the Full Analysis Set (FAS), which is defined as those subjects who received at least one dose of tofacitinib plus MTX during the open label period and were randomized and received at least one dose of the randomized investigational drug (tofacitinib MR 11mg QD with placebo for MTX or tofacitinib MR 11mg QD with MTX) during the blinded MTX withdrawal period.

A robustness analysis based on a per-protocol analysis set will be performed. Sensitivity analyses using different methods of handling missing data will also be conducted; further details will be outlined in the SAP.

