Appendix 1.2. Definition and Use of Visit Windows in Reporting

Visit windows will be used for efficacy variables, and for any safety displays that display by week.

If more than one observation from the same subject falls into the same visit window, the value closest to the targeted day will be used as the observation for that week. If two visits are equal distant from the Targeted Day in absolute value, the later visit should be used. All observations will, however, be included in the listings.

For endpoints derived from multiple components, eg, DAS28-4(ESR), each component will be windowed to select the value for analysis at a specific visit, and the value of the endpoint will then be derived. This means the component values may be from different visit dates that fall within the analysis window.

Subjects’ observations will be excluded from visit windows if the data was collected more than 7 days off study drug. (Safety analysis may follow Pfizer standard.)

Visit Label	Targeted Day	Analysis window for data sets
Open-Label Run-In Phase		
Baseline	Day 1	Last Observation up to and including First Dosing Date (no earlier than Day -90)
Week 6	Day 42	Days 2 – 63
Week 12	Day 84	If there is Week 6 visit such as lab tests: Days 64 – 126; If no Week 6 visit: Days 2 – 126
Week 24	Day 168	Day 127 – Discontinuation Day /Randomization Day (the earlier one)
Double-Blind Phase		
Randomization (Week 24)	Randomization Day	Last Observation up to and including First Dosing Date in Double-Blind Phase (no earlier than Day 127)
Week 36	Randomization Day + 84	Randomization Day + 1 – Randomization Day + 126
Week 48	Randomization Day + 168	Randomization Day + 127 –

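### The 90% power stated for 232 subjects randomized is in effect the power with complete Week 48 data; no allowance is stated for loss between Weeks 24 and 48

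*Protocol*

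**What the plan says.** Protocol 9.1 states that "a sample size of approximately 232 subjects randomized at Week 24 would provide 90% power to declare non-inferiority", with a two-sided 5% error, SD 1.4 and margin 0.6. The Statistical Methods part of the Protocol Summary repeats it: "a sample size of 232 subjects randomized at Week 24 would provide 90% power to declare non-inferiority". Neither place states the true difference assumed, nor whether 1.4 is before or after covariate adjustment.

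The one attrition rate in the plan is in the same section: "factoring in a discontinuation rate of approximately 15% during the open label run-in phase". It links about 680 enrolled to at least 232 randomized, at an assumed 40% low disease activity (LDA) rate.

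The primary endpoint is read 24 weeks after randomization. In that interval the plan provides for loss:

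- Protocol 6.3: "If a subject has discontinued investigational product for greater than 14 consecutive days, the subject will be discontinued from the study". It also removes subjects whose flare rescue cannot control.
- Protocol 7.23 lists among the reasons for withdrawal "Serious infections defined as any infection (viral, bacterial, or fungal) requiring parenteral antimicrobial therapy or hospitalization for treatment" and "Use of rescue medications for more than 10 consecutive days".
- SAP Appendix 1.2: "observations will be excluded from visit windows if the data was collected more than 7 days off study drug".

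The primary analysis (Protocol 9.3.1, SAP 5.2.2) is an MMRM with "prior use of a biological DMARD, and baseline DAS28-4 (ESR) value as a covariate". Missing values are treated as missing at random.

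**The concern.** A reader will take 90% as the power of a trial that randomizes 232 subjects and then loses some of them. If the figure in fact assumes that practically all 232 contribute a Week 48 value, the stated power is higher than 232 randomized subjects would deliver on the plan's own inputs. The sponsor raised enrolment from 580 to 680 to absorb run-in losses, so it accepted that attrition needs an allowance. That allowance stops at randomization.

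What is at stake is an accurate statement of the risk that a truly non-inferior regimen misses the margin. The validity of the non-inferiority conclusion is not affected.

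**Working it through.** **Inputs from the documents.** Margin 0.6; SD 1.4; two-sided 5% (z = 1.96); 232 randomized 1:1, so n = 116 per arm (Protocol 9.1 and Section 3). Non-inferiority requires the upper 95% confidence bound to be below 0.6 (SAP 5.1).

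**Assumptions.** True difference 0, because none is stated. SD 1.4 is taken as the per-subject SD of change in each arm. Section 9.1 attaches 1.4 to the difference between arms; read literally, as the SD of a single between-arm difference, that would need only 58, so the per-subject reading is the one that yields 232.

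**1. Reproduce the plan's figure.** Power = Φ(0.6 / (1.4 × √(2/n)) − 1.96).

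At n = 116: standard error = 1.4 × √(2/116) = 0.1838; 0.6/0.1838 = 3.264; Φ(1.304) = 90.4%. The noncentral t gives 90.2%.

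**2. Find the reserve.** n for exactly 90% = 2 × (1.4 × (1.96 + 1.282)/0.6)² = 114.4 per arm (normal), or 115.4 (t). Tolerated loss is 1 − 114.4/116 = 1.4%, or 1 − 115.4/116 = 0.5%. In whole subjects, 115 per arm gives 89.9% on the t basis. So 232 is the complete-data requirement, give or take two subjects.

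**3. Locate the 15%.** 680 × 0.85 × 0.40 = 231. The allowance is used up in reaching the randomization target.

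**4. Illustrate loss after randomization.** The documents give no rate, so these are assumed, equal in both arms, with 1.4 taken as the SD the model achieves. Loss means no eligible value in the Week 48 window. The completer column puts n = 116 × (1 − loss) into the formula of step 1.

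The MMRM column uses the variance of a Week 48 mean under monotone missingness, 1.4² × ((1 − r²)/n48 + r²/n36). Here n48 = 116 × (1 − loss) and n36 = n48 + f × 116 × loss, with assumed r = 0.5–0.7 (Week 36–48 correlation) and f = 0.5–1 (share of dropouts with Week 36 data).

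| Loss | n per arm | Completers, normal (t) | MMRM using Week 36 |
|---|---|---|---|
| 5% | 110.2 | 88.9% (88.6%) | 89.1–89.6% |
| 10% | 104.4 | 87.2% (86.9%) | 87.6–88.8% |
| 15% | 98.6 | 85.3% (85.0%) | 86.0–87.8% |

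**5. Offsets.** If 1.4 is unadjusted, the correlation between covariates and change that restores 90.0% on completers is √(1 − n/114.4) = 0.19, 0.30 and 0.37 at 5, 10 and 15% loss. If more are randomized, the LDA rate that offsets the loss is 232/(1 − loss)/(680 × 0.85) = 42%, 45% and 47%. At the early 79% LDA rate, 680 × 0.85 × 0.79 = 457 would be randomized, and even 20% loss would leave 98.4% power.

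**6. The zero difference.** With no loss, a true difference of 0.05 leaves 0.55 of the margin and gives 84.9%; 0.10 leaves 0.50 and gives 77.6%. The condition therefore belongs beside any power figure.

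**The case against.** The calculation itself is correct, and several things work in the plan's favour.

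- **More than 232 may be randomized.** Section 9.1 aims for at least 232, and no cap on randomization is stated. Section 3 reports an LDA rate of about 79%. This has weight: the shortfall exists only near the 40% assumption. But the protocol calls that rate a small-sample figure, 9.1 still plans on 40%, and a possible surplus does not change what 232 delivers.
- **MMRM uses Week 36.** It does, and the table shows the gain. It recovers part of the lost information, so every MMRM figure there stays below 90%.
- **Covariates may lower the SD.** This could cancel the loss entirely. Section 9.1 does not say whether 1.4 already includes that gain, so a reader cannot count on it.
- **Loss may be small.** Randomized subjects have completed 24 weeks and reached LDA. Not every withdrawal loses its value: under SAP Appendix 1.2, a withdrawal visit within 7 days of the last dose can still count, for Week 48 if it falls after Randomization Day + 126 and otherwise for Week 36. Nor is it settled that a subject removed under the 14-day rule is always excluded. Tofacitinib and MTX are both investigational products, and the SAP does not say whether stopping only one of them counts as off study drug. The loss rates above are therefore illustrations.

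A reader might infer that 90% fails unless every one of the 232 supplies Week 48 data. That is too strong: the normal approximation tolerates 1.4% loss, and covariate adjustment might tolerate more. A reader might also infer that the trial is underpowered or needs more patients. The documents do not support that, since they fix neither the loss rate, nor the type of SD, nor the number finally randomized.

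**Conclusion.** The point holds as one of incomplete statement. On the plan's own inputs, 232 is essentially the complete-data requirement for 90% power, and nothing is set aside for the 24 weeks in which the protocol itself requires withdrawals.

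The size is modest. At 5–15% loss, power at 232 randomized is about 1 to 5 points below 90% on completers, and about 0.4 to 4 points below with MMRM recovery. This rests on a true difference of 0, equal loss in both arms, 1.4 being the SD that the model achieves, and, for the MMRM figures, the assumed correlation and share of dropouts with Week 36 data. It disappears if covariates explain enough variance or clearly more than 232 are randomized. The confidence-bound decision rule is unaffected.

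**What to change.** In Protocol 9.1 and in the Protocol Summary:

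1. Tie the 90% to approximately 232 subjects with Week 48 data.
2. Describe 1.4 as the per-subject SD of change in each arm; the sponsor should say whether it is before or after covariate adjustment.
3. State the assumed true difference of 0.
4. Add one sentence giving the sponsor's expected loss between Weeks 24 and 48 and the resulting power for 232 randomized. If the run-in rate of 15% were carried over, that would be about 85–88%.

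No change to enrolment, margin, analysis or decision rule is proposed. The cost is a slightly less favourable stated power. Because this edits the protocol and amendments need ethics approval, the change can be made at the next amendment.

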9.2. Descriptive Analysis

Patient and clinical characteristics at baseline and randomization (ie, the end of open-label phase) will be summarized with the use of descriptive statistics. Frequencies and percentages will be used to describe categorical variables and mean and standard deviations (or median with interquartile range [IQR] and range, where appropriate) will be calculated for continuous variables.

Descriptive statistics will also be provided for all efficacy and safety endpoints at each visit in open-label phase or double-blind withdrawal phase as appropriate. Further details will be outlined in the SAP.

9.3. Efficacy Analysis

9.3.1. Analysis of the Primary Endpoint

The primary endpoint of change from randomization in DAS28-4(ESR) at Week 48 will be analyzed as a continuous variable using a linear mixed-effect model of repeated measures (MMRM) that includes the fixed effects of treatment, visit, treatment-by-visit interaction, prior use of a biological DMARD, and baseline DAS28-4 (ESR) value as a covariate. Within-subject variability will be accounted for using a random effect with an unstructured covariance matrix. Change from randomization at any visit post-randomization will be defined as the DAS28-4 (ESR) value at that visit minus the value at randomization.

The primary analysis will be a non-inferiority test to show that tofacitinib MR 11mg QD monotherapy is not less effective (non-inferior) than tofacitinib MR 11mg QD with MTX within the margin of non-inferiority set at 0.6 (ie, the difference in mean change from randomization in DAS28-4 (ESR) between the two arms). In other words, the change from randomization in DAS28-4(ESR) for the tofacitinib MR 11mg QD monotherapy arm may be less favorable than that for the tofacitinib MR 11mg QD with continued MTX arm by no more than 0.6. The estimated treatment difference and the associated 95% confidence interval (CI) will be presented. If the upper bound of the 95% two-sided CI for the difference (tofacitinib monotherapy arm minus tofacitinib with MTX arm) in change from randomization in DAS 28-4 (ESR) between the two arms is lower than 0.6, then tofacitinib monotherapy will be declared to be non-inferior to the tofacitinib with continued MTX treatment.

The analysis will be based on the Full Analysis Set (FAS), which is defined as those subjects who received at least one dose of tofacitinib plus MTX during the open label period and were randomized and received at least one dose of the randomized investigational drug (tofacitinib MR 11mg QD with placebo for MTX or tofacitinib MR 11mg QD with MTX) during the blinded MTX withdrawal period.

A robustness analysis based on a per-protocol analysis set will be performed. Sensitivity analyses using different methods of handling missing data will also be conducted; further details will be outlined in the SAP.

